Effectiveness of Ultrasound Guided Platelet Rich Plasma Injections in the Sacroiliac Joint
NCT03122119
April 25, 2023

Protocol Synopsis for Research Project Involving Human Subjects

PROTOCOL INFORMATION

Title of Research Activity: Effectiveness of Ultrasound Guided Platelet Rich Plasma Injections in the Sacroiliac Joint

A. Specific Aims

The objective of this research is to identify the effectiveness of Platelet-Rich Plasma (PRP) injections into the sacroiliac (SI) joint in relieving low back pain.

B. Experimental Design and Methods

The research design for this study will be a prospective clinical trial evaluating the improvement in low back pain secondary to SI joint dysfunction pre and post PRP injection. No control group will be utilized in our study due to the ethics of research in withholding treatment to patients. Patients who are found to be candidates will be offered the PRP injection without cost until the number of available donated kits is exceeded. Each subject will serve as their own control by reporting pre-injection pain levels as well as pain levels immediately post-injection, 2 weeks, 4 weeks, 3 months, and 6 months post-injection.

Our hypothesis is, "Platelet-Rich Plasma Injections in the Sacroiliac Joint using ultrasonography in conjunction with physical examination and Point of Maximal Tenderness will produce statistically significant pain relief for more than 3 months as measured by the Numeric Rating Scale for Pain (NRS)."

Experimental design will be a nonrandomized trial (or quasi-experiment). The specific study design to be used is pretest-posttest design. The independent variable will be the PRP injection. The dependent variables of interest include the NRS and Oswestry Disability Index (ODI) recording pre-injection, immediately post-injection, 2 weeks, 4 weeks, 3 months, and 6 months, post-injection.

1) Methods and Procedures

Data in this study will be collected quantitatively by assessing the patient's pain prior to the injection as well as at 2 weeks, 4 weeks, 3 months, and 6 month follow up using the NRS and ODI.

2) Data Analysis and Data Monitoring

The following data will be recorded from each patient: current pain scale using the NRS and their functionality using the ODI.

Study Protocol

Summary

We would like to analyze and obtain confidence intervals and mean reduction of NRS and ODI for the following:

Confidence Interval for the following (for both NRS and ODI):

1. Baseline – 2wks
2. Baseline – 4wks
3. Baseline – 3 months
4. Baseline – 6 months

Statistical Analysis Plan

The Oswestry Disability Index (ODI) uses a questionnaire to assess pain levels and the impact pain has on a patient's daily life. This was chosen as the primary outcome measure and was calculated based on a questionnaire then converted to a percentage for objective comparison.

The secondary outcome measure was the Numeric Rating Scale for Pain (NRS). This rating scale provided another objective tool based purely on pain severity for comparison of changes in pain levels pre- and post-injection.

Statistical analysis was performed using SPSS 25, XLStat 2019.1.2, and R3.5.2. Variables were assessed for normality of distribution by using the Shapiro-Wilk test and Jarque-Bera test. ODI and NRS scores were compared from baseline to 2 weeks, 4 weeks, 3 months, and 6 months using ANOVA and paired ttest. Discrete variables were summarized as means and standard deviations.

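### The aim and hypothesis credit PRP with the pain relief, but the disclosed single-arm pretest-posttest design can only estimate change from baseline

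*Combined protocol and SAP*

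**What the plan says.** Under A. Specific Aims the plan states: "The objective of this research is to identify the effectiveness of Platelet-Rich Plasma (PRP) injections" into the sacroiliac joint for low back pain. The title uses the same term. Under B. Experimental Design and Methods, the hypothesis is that the injections "will produce statistically significant pain relief for more than 3 months", measured on the NRS.

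Section B is also open about the design. It says "No control group will be utilized in our study", giving the ethics of withholding treatment as the reason, and "The specific study design to be used is pretest-posttest design". On the comparator it says: "Each subject will serve as their own control by reporting pre-injection pain levels", followed by later scores. It also says "The independent variable will be the PRP injection". On entry it says only "Patients who are found to be candidates will be offered the PRP injection", free of charge while donated kits last.

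The Summary under Study Protocol asks for mean reductions and confidence intervals for NRS and ODI from baseline to 2 weeks, 4 weeks, 3 months and 6 months. The Statistical Analysis Plan names ODI as primary and NRS as secondary, and compares both with baseline by ANOVA and paired t-test. It is written in the past tense. Neither part says that the change cannot be attributed to PRP.

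**The concern.** To say that an injection produces relief is to compare the patient's pain after it with what the pain would have been without it. A pre-injection score is a baseline. It does not show what the patient would have reported at 3 or 6 months untreated.

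The hypothesis is framed around statistical significance. If the NRS comparisons are significant, the natural report is that the hypothesis is supported, and as worded it says that PRP produced the relief. The same result could arise with no PRP effect. What is at stake is the conclusion attached to the estimates, not the estimates themselves.

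**Working it through.** The plan states no sample size, power, SD, effect size or entry threshold, so there is no figure to reproduce. The check compares what the wording claims with what the analysis identifies.

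**1. What is claimed.** The aim and the hypothesis (sections A and B) both concern an effect of PRP. Call the mean effect at visit t, PRP against no PRP, τ(t).

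**2. What is estimated.** The Summary and the Statistical Analysis Plan contain only baseline-to-visit comparisons. Call the mean reduction from baseline Δ(t). It splits as

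Δ(t) = τ(t) + ν(t),

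where ν(t) is the mean reduction that the same patients would have shown by visit t without PRP.

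**3. What the tests address.** The paired t-test and the interval concern Δ(t) = 0. They bear on τ(t) = 0 only if ν(t) is zero or known.

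**4. Whether the plan supplies ν(t).** It describes no concurrent or historical comparator, no benchmark, and no run-in or repeated baseline. All patients receive PRP, so exposure differs only between before and after and cannot be separated from time. Natural course, expectation and other treatment all enter ν(t). Regression to the mean enters too if patients are selected when pain is high; the plan gives no entry rule from which to tell.

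**5. Whether ν(t) can be sized.** It cannot. An illustration shows how far the answer depends on inputs that must be assumed. With no PRP effect and a non-PRP drop of d SDs of change, the chance that one visit shows a significant improvement (two-sided 0.05) is the probability that a noncentral t variable, with n − 1 degrees of freedom and noncentrality d√n, exceeds the upper 2.5% point of t. For d = 0.4 and n = 30, d√n = 0.4 × 5.477 = 2.19, which gives 56%.

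| d (assumed) | n = 20 | n = 30 | n = 50 |
|---|---|---|---|
| 0 | 2.5% | 2.5% | 2.5% |
| 0.2 | 13% | 18% | 28% |
| 0.4 | 40% | 56% | 79% |

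For regression to the mean alone, assume NRS with mean 5 and SD 2, rounded to 0–10, correlation 0.5 or 0.7 between scores at baseline, 3 and 6 months, and no PRP effect or other trend. Simulated results, requiring significance at both 3 and 6 months, with n = 20 to 50:

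- No entry threshold: mean drop 0; both visits significant in 0.5% or less.
- Entry at NRS 6 or above: mean drop 0.62 points (correlation 0.7) or 1.00 point (correlation 0.5); both significant in 24% to 94%.

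A range from under 1% to 94% reflects the assumptions. It shows that significance alone does not isolate a PRP effect; it does not measure bias in this trial.

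**The case against.** The strongest reply is that nothing is hidden. The plan says that there is no control group, calls the study nonrandomized or quasi-experimental, names the pretest-posttest design, and already asks for the quantities such a design can deliver: mean reductions with confidence intervals. It reports no causal conclusion. The ethical reason explains why no untreated group exists. On this view what remains is the usual single-arm caveat.

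Much of that stands. The design choice is not the fault, and no control arm is being asked for. The own-control phrase is explained in its own sentence as the use of pre-injection scores, and calling PRP the independent variable is conventional in a before-after study; neither carries the point by itself. The title merely echoes the aim.

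The reply does not answer the aim and the hypothesis. Disclosing the design does not limit what the hypothesis asserts, and an ethical reason for having no control does not make the change attributable to PRP.

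A further fair objection is that rewriting a hypothesis after the results are known is undesirable even when disclosed. The Statistical Analysis Plan's past tense makes this a live possibility, and the fix allows for it.

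**Conclusion.** The concern holds as a mismatch between causal wording and a design that estimates change, and it should be corrected. It rests on two facts in the documents: every patient receives PRP, and every planned comparison is with baseline. It needs none of the assumed figures.

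Its reach is limited. No stated number or analysis is shown to be wrong, and mean change with its interval remains a legitimate result for both scales.

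A reader might infer three stronger things that the documents do not support:

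- *That the plan treats a significant change as proof of effectiveness.* No passage states such a rule; the risk lies in how the hypothesis is worded.
- *That an improvement here would be mostly regression to the mean or placebo response.* The documents give no entry rule, sample size or SD, so the non-PRP change cannot be sized, and it could be nil.
- *That PRP does not work.* The design cannot show this either.

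**What to change.** (a) Whatever the stage, add a statement such as: *The analysis estimates mean change in ODI and NRS from baseline to 2 weeks, 4 weeks, 3 months and 6 months after PRP in an uncontrolled cohort. Without a concurrent control, this change cannot be attributed to PRP.*

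(b) If the analysis has not been done, reword the aim and hypothesis to match and keep the duration criterion, for example: *Mean NRS will be lower than baseline at 3 and 6 months after PRP.* Clarify that the own-control phrase means the pre-injection score used as baseline.

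(c) If the analysis is finished, leave the hypothesis and its duration criterion as recorded. Limit the report's conclusion to change from baseline and do not claim effectiveness.

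This needs no new patients, data or analyses. The price is a more modest claim.

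### As the SAP reads, the 3- and 6-month paired t-tests use only patients who return; one likelihood model on all observed visits would guard those reductions when return depends on earlier response

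*Combined protocol and SAP*

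**What the plan says.** The Statistical Analysis Plan names the method in one sentence: "ODI and NRS scores were compared from baseline to 2 weeks, 4 weeks, 3 months, and 6 months using ANOVA and paired ttest". Of the ODI it says "This was chosen as the primary outcome measure"; the NRS is secondary. The Study Protocol Summary sets the output: "We would like to analyze and obtain confidence intervals and mean reduction of NRS and ODI for the following", and lists baseline against each of the four follow-up times.

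Section B (Experimental Design and Methods) schedules both scores repeatedly: "recording pre-injection, immediately post-injection, 2 weeks, 4 weeks, 3 months, and 6 months, post-injection". The Methods and Procedures text and the SAP keep the four later follow-ups and leave out the immediate post-injection score. Section B also says "No control group will be utilized in our study", and its hypothesis is that the injection "will produce statistically significant pain relief for more than 3 months as measured by the Numeric Rating Scale for Pain (NRS").

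Neither part of the document states an analysis set, an imputation rule, the type of ANOVA, an expected dropout rate or a sample size.

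**The concern.** A paired t-test can use a patient only if both scores exist. With no imputation stated, the natural reading (an inference, since the text is silent) is that the 3-month test uses patients scored at 3 months and the 6-month test uses those scored at 6 months. A patient who came at 2 and 4 weeks and then stopped contributes nothing to either, although the earlier scores say something about how that patient was doing.

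The ANOVA may rest on yet another set of patients. A classical repeated-measures ANOVA drops anyone with a missed visit. One fitted by likelihood would not, but none is stated.

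The claim of relief beyond 3 months rests on the two latest visits, where losses have had most time to build up. If return is related to response, the late means and confidence intervals describe a selected group, and a change from one visit to the next may partly be a change in who was measured. In a single-arm design no comparison group absorbs any of this. The bias can run either way: upwards if poor improvers stay away, downwards if patients who feel well do.

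**Working it through.** The plan has no figure to reproduce: it states no n, SD, correlation, effect size or dropout rate. **Every input below is assumed**, so the results are an illustration.

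**Set-up (NRS scale).** Baseline and four follow-ups, multivariate normal, SD 2 at each visit, correlation r = 0.6, true reduction 2.0 at every follow-up, n = 40, 3,000 simulated trials per scenario. The SD of change is 2 × √(2 × (1 − 0.6)) = 1.79. Patients may leave before the 4-week, 3-month or 6-month visit and do not come back. The chance of leaving takes one of two values, depending on whether improvement at the previous visit was above or below a cut. In the mildest case (5% or 15%, cut at the mean) the average is 10% per visit, so 1 − 0.9³ = 27% are missing at 6 months. In the steepest case, 40% of patients on one side of the cut leave at each visit and nobody on the other side does.

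**Two estimates.** Returners: the mean change among patients scored at that visit, which is what the paired t-test estimates. Likelihood: the mean change from one multivariate normal model on all observed scores, fitted by sequential regressions, which is exact for this dropout pattern.

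| Who leaves | Missing at 6 months | Returners, 3 months | Returners, 6 months | Coverage of returners' 95% CI, 6 months | Likelihood |
|---|---|---|---|---|---|
| Poor improvers (5 scenarios) | 24–32% | 2.08–2.26 | 2.11–2.37 | 94% mildest, 78% lowest | 1.99–2.00 |
| Improvers (4 scenarios) | 27–32% | 1.74–1.93 | 1.62–1.89 | 94% mildest, 80% lowest | 2.00–2.01 |
| Unrelated to response | 33% | – | 2.00 | – | 2.00 |
| Either direction, low dropout | 8–10% | – | 2.06–2.09 or 1.92–1.94 | 93–94% | – |

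**In SD units.** At 6 months the bias runs from (2.00 − 1.89)/2 = 0.05 to (2.00 − 1.62)/2 = 0.19 SD; at 3 months it is 0.04–0.13 SD. If the ODI SD is 10–20 points (assumed), the 6-month bias is 0.05 × 10 = 0.5 to 0.19 × 20 = 3.8 ODI points. No scenario reverses the sign of the reduction.

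**Dependence on n and r.** In the steepest case the returners' 6-month interval covers the truth in about 88%, 80% and 71% of trials at n = 20, 40 and 60, in both directions: the interval shrinks while the bias stays. The likelihood interval covers in 94–97% at n = 20 and 40. From mildest to steepest case, returners at 6 months show 2.14–2.50 or 1.86–1.52 at r = 0.4, and 2.08–2.22 or 1.92–1.78 at r = 0.8.

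**If the ANOVA is listwise.** Even the 2-week reduction shifts, to 2.15–2.50 or 1.50–1.85, against 2.00 from the paired test. The two named methods would then disagree at a visit nobody missed.

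**A second set of assumptions (ODI scale).** SD 15, correlation 0.5–0.7, true reduction 12 points, 23–45% lost by 6 months, with loss depending on change at the previous visit and poorer responders leaving. The paired analysis overstates the reduction by 0.5–1.9 points at 3 months and 0.9–3.4 at 6 months; the likelihood model is off by at most 0.1. With no dropout the two estimates are identical.

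**Limit of the model.** If leaving depends on the score that is never seen, the model reduces the bias without removing it. Take zero true change, SD of change 2.5, with 40% leaving if worse and 10% if better. Mean |change| is 2.5 × 0.798 = 1.995, so returners show (0.5 × 0.9 − 0.5 × 0.6) × 1.995 / 0.75 = 0.40. Conditioning on one earlier visit with correlation r leaves about 0.40 × (1 − r²): 0.34, 0.26 and 0.14 at r = 0.4, 0.6 and 0.8. In the ODI set-up, loss of this kind gives a 6-month bias of 1.4–5.1 points for the paired test and 0.7–2.8 for the model.

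**The case against.** The harm needs three things at once: missed late visits, return related to response, and an available-case analysis. The documents establish none of them; the third is inferred from a short paragraph, and an ANOVA fitted by likelihood would escape the problem. On this view the real defect is under-reporting, and the remedy is to state the handling and the counts rather than replace the tests. This stands as a limit on what can be claimed, but not against the change: as written, the paired test is the stated method, no alternative handling is given, and the model returns the same mean reductions when follow-up is complete.

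The lowest coverage figures come from steep dropout rules. That is correct: in the mildest case, with 27% missing, coverage is still about 94%, so weak dependence does the interval little harm.

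The near-perfect likelihood result is built in, because dropout was made to depend on observed scores. This also stands. Loss driven by unseen scores leaves roughly 35–85% of the bias in the example above, which is why a sensitivity analysis belongs in the fix.

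At small n the gain is modest. At n = 20 the root mean squared error at 6 months is about 0.49 for returners against 0.47 for the model in the mildest case, and 0.58 against 0.54 in the steepest. At n = 40 in the steepest case it is about 0.50 against 0.35. The model was no worse in any case checked.

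Finally, the SAP reports its analysis in the past tense ("Statistical analysis was performed using SPSS 25, XLStat 2019.1.2, and R3.5.2"), so a new model may be post hoc and cannot repair pre-specification.

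**Conclusion.** The concern holds, conditionally. Followed as written, the late paired tests leave out non-returners and discard their scheduled 2- and 4-week scores, although the central claim rests on those late visits. Under the assumed inputs with 24–32% missing at 6 months, the distortion is 0.05–0.19 SD in either direction, with interval coverage at n = 40 falling from near nominal to about 80% as the link between return and response strengthens. At 8–10% missing it is minor, and with full follow-up it is nil. It does not reverse the direction of effect in any scenario examined. The real size cannot be judged from the documents, which give neither n nor dropout. The protection is against return that depends on earlier observed scores; it is partial if return depends on unseen ones, and it does nothing about the missing control group.

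**What to change.** 1. For both ODI and NRS, include every injected patient with a baseline score.
2. Replace the separate paired t-tests and the unspecified ANOVA with one likelihood-based repeated-measures model per outcome, using all observed scores at baseline and the SAP's four follow-up visits. Use an unstructured covariance where it can be fitted and name a simpler fallback. Report the mean reduction and 95% CI at each visit.
3. Report the number of patients scored at each visit. This alone shows readers whether the concern applies.
4. Only if scores are missing at 3 or 6 months, add a simple sensitivity or tipping-point analysis with no fixed minimum shift. For example, with n = 40, SD of change 1.79, missing fraction m and observed reduction d, the lower 95% limit reaches zero when missing patients worsen on average by [(1 − m)d − h]/m, where h is the returners' CI half-width. For d = 1.0 this is 2.9, 0.8 and about 0 points at m = 10%, 20% and 30% (h = 0.61, 0.65, 0.69); for d = 2.0 it is 11.9, 4.8 and 2.4.
5. If the analysis has already been done, label steps 2 and 4 post hoc.

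The cost is SAP wording, one model per outcome and perhaps one sensitivity analysis; no new data are needed. The downsides are a possibly less favourable late estimate and usually wider intervals: in the simulation, from 1% narrower to 11% wider than the returners' at n = 40, and 2–29% wider at n = 20, where the simpler covariance may be needed.

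### The SAP names no primary visit, testing order or role for the ANOVA: at an assumed 5% per test, the false-positive risk is about 16–19% for the four ODI visits and 13–34% for all eight comparisons

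*Combined protocol and SAP*

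**What the plan says.** The Statistical Analysis Plan ranks the two outcomes. Of ODI it says "This was chosen as the primary outcome measure and was calculated based on a questionnaire", and it labels NRS secondary. Its testing rule is one sentence: "ODI and NRS scores were compared from baseline to 2 weeks, 4 weeks, 3 months, and 6 months using ANOVA and paired ttest". Two outcomes at four visits make eight comparisons with baseline.

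The Summary under Study Protocol asks for mean reductions and confidence intervals for the same eight contrasts and gives no confidence level.

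The hypothesis, in section B (Experimental Design and Methods), is about NRS, not ODI. It predicts "statistically significant pain relief for more than 3 months".

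Neither part of the document gives a significance level, a primary visit, an order of testing or a multiplicity adjustment. Nor does it say whether the ANOVA must be significant before the paired t-tests are read.

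**The concern.** Success is framed as statistical significance, and the plan leaves open which significant result counts. Within the primary outcome the four visits have no ranking. Across outcomes, the SAP points to ODI and the hypothesis to NRS, so success could be claimed on either scale. A single significant result at one visit could be reported as support, including one at 2 or 4 weeks, which cannot show relief lasting beyond 3 months. The risk of such a result arising by chance is then higher than the level used for each test.

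**Working it through.** **Figure to reproduce.** None. The documents state no alpha, error rate, power or sample size.

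**Inputs from the documents.** Two outcomes; four follow-up visits; all changes within an outcome share one baseline; ODI primary, NRS secondary.

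**Assumptions.** Two-sided 5% per test; no true mean change; any significant result counts; correlation between the change scores of one outcome 0 to 0.9; correlation between outcomes 0 to 0.9; n from 10 to 50 for the t-test simulations.

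**Why 0.5 is a natural central value.** Let each change be D_j = Y_j − Y_0, with equal variances σ² and equal correlation ρ over time. Then Var(D_j) = 2σ²(1 − ρ), and Cov(D_j, D_k) = σ²(ρ − ρ − ρ + 1) = σ²(1 − ρ). The correlation between two changes is therefore 1/2, whatever ρ is.

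**Step 1: no ANOVA gate.** For k independent tests the risk is 1 − 0.95^k:
- k = 4: 1 − 0.95⁴ = 18.5%
- k = 8: 1 − 0.95⁸ = 33.7%

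For correlated tests (multivariate normal simulation, 300,000 draws):

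| Correlation between changes | Four ODI visits | All eight, over between-outcome correlation 0 to 0.9 |
|---|---|---|
| 0 | 18.5% | 33.7% down to 25.3% |
| 0.5 | 15.6% | 28.8% down to 21.2% |
| 0.7 | 12.9% | 24.3% down to 17.7% |
| 0.9 | 9.4% | 17.8% down to 12.9% |

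At correlation 0.5, all eight tests give 24–29% for between-outcome correlations from 0 to about 0.75. Simulated paired t-tests at n = 10 to 50 agree: about 16% for ODI and 25–30% for all eight (between-outcome correlation 0 to 0.7).

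**Step 2: only false results towards relief.** At correlation 0.5 these are 7.8% for the four ODI visits and about 12–15% for all eight (between-outcome correlation 0 to 0.7), against 2.5% for one test.

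**Step 3: ANOVA as a gate, nothing changes.** Suppose the t-tests for an outcome are read only if its repeated-measures ANOVA is significant at 5%. The risk falls to about 4% for ODI and 6–8% across both outcomes.

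**Step 4: ANOVA as a gate, real change at 2 and 4 weeks only.** With an early change of 1 SD, n = 30 and correlation 0.5, the ANOVA is almost always significant. The two later tests are then effectively ungated. The simulated risk of a false result at 3 or 6 months is about 9% for ODI. Across both outcomes it is about 17% if they are uncorrelated, which agrees with 1 − (1 − 0.09)² = 17.2%, and about 14% at a between-outcome correlation of 0.7.

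**Step 5: effect of a correction.** Holm across eight begins at 0.05/8 = 0.00625. In simulation with no true change (n = 30) it gave about 4–5%.

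**The case against.** The strongest counter-case has four parts.

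- **The outcomes are ranked.** A reader might infer that all eight comparisons stand equal. The SAP does not support that, because it puts ODI first. The main family is the four ODI visits, at about 16–19% for correlation 0.5 to 0. What remains is that the visits within ODI are unranked, and that the NRS hypothesis weakens the ranking.
- **No error level is stated.** A reader might infer that the plan promises 5% and breaks that promise. It promises no level; 5% is an assumption made here.
- **The ANOVA may be intended as a gate.** An omnibus test followed by paired comparisons is a natural reading of "using ANOVA and paired ttest", and it would remove most of the inflation when nothing changes. The documents do not say so, however, and step 4 shows that the protection fails at the visits nearest the hypothesis if there is real early change.
- **The hypothesis limits what counts.** An isolated 2-week result would not satisfy a claim about more than 3 months. That is fair, but nothing in the SAP prevents such a result from being reported as significant.

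One might also extend the complaint to the eight confidence intervals. The Summary asks for them as estimates, and unadjusted intervals are acceptable in that role. They add to the problem only if excluding zero is read as a test.

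**Conclusion.** The concern holds as a gap in specification. The plan has no primary visit, no order or adjustment and no role for the ANOVA, and its hypothesis and primary outcome disagree. With an assumed two-sided 5% per test, no true change and no gate, the risk of at least one false significant result is about 16–19% for ODI (about 9% at correlation 0.9) and about 13–34% for all eight. The risk in the direction of relief is about half of the correlated figures.

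Quoting 24–29% as the plan's error rate would be too strong. That range needs a correlation near 0.5, all eight tests in one family and no gate, none of which the documents state. Treating the ANOVA as a full remedy would be too generous: with real change only at 2 and 4 weeks, the gated risk at 3 or 6 months is still about 9% for ODI and 14–17% across both outcomes.

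**What to change.** 1. Reconcile section B with the SAP: decide whether ODI or NRS is primary. No testing order can be set before this.
2. State alpha, sidedness and the role of the ANOVA.
3. Test in a fixed order, each step at two-sided 5%, stopping at the first non-significant result: the primary outcome at 6 months, then at 3 months, then the other outcome at 6 months and at 3 months. Six months comes first because it is the only planned visit later than 3 months.
4. Report 2- and 4-week results as mean reductions with confidence intervals and no significance claim.
5. If no order is chosen, or results have already been seen, use Holm across the eight comparisons. The SAP's past tense suggests that the analysis may have been done but does not establish it. An order written after seeing results gives no error control and would have to be labelled post hoc.

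**Cost.** The change is to wording only and needs no new data. Under the fixed order the first test loses no power, but the 2- and 4-week comparisons lose confirmatory status, and a non-significant 6-month result blocks every later claim. Whichever outcome is placed second can be claimed only if the other succeeds at both visits. Holm costs some power, since the smallest p-value must be below 0.00625.
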